Instruments: assessing Long COVID symptoms. While there is no symptom or HRQOL instruments designed for COVID-19 survivors or patients with infectious disease, some HRQOL instruments designed for cancer patients may be an alternative choice. Specifically, as it is mentioned earlier in this proposal, in addition to respiratory symptoms, Long COVID seems to be systematical— just like symptoms caused by cancer and its treatment. Thus we propose to use European Organization for Research and Treatment of Cancer Quality of Life questionnaire (EORTC-QLQ

C30, Taiwan Chinese version) and lung cancer model (EORTC QLQ-LC29, Taiwan Chinese version) to measure Long COVID. In fact, among the 36 Long COVID self-perceived symptoms reported by Lopez-Leon's systematical review and Romero-Duarte's 6 months follow-up, these two questionnaires covered 29 of them (about 81%), including the most frequently reported ones (table 1). Three missing symptoms that are not covered by EORTC-QLQ-C30 or LC29 are anosmia, ageusia, and palpitation. These symptoms will be checked for existence separately during the follow-ups.

Both EORTC-QLQ C30 and LC29 are widely used by medical research and show good validity and reliability. EORTC-QLQ C30 consists of 30 items and measures patients' functions and symptoms by 4-point Likert scales. EORTC-QLQ C30 also measures quality-of-life (QoL) by 7-point Likert scales. While LC29 consists of 29 items, the subscales of 'fear of progression (2 items)' and 'surgery-related problems (5 items)' will not be used as they are related to cancer progression and treatment. The remaining 22 items will be rated by 4-point Likert scales in this study to measure additional symptoms. The Cronbach's alpha coefficient are above 0.70 and 0.73 for all items in EORTC-QLQ C30 and LC29 Taiwan Chinese version, respectively [21-23]. Higher scores for symptom scales represent more intense symptoms while higher scores for function scales and QoL means better function and QoL level. Example questionnaires are provided in appendix A and B.

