Statistical methods. In addition to use descriptive statistics to describe the characteristics of participants and symptoms, one-way repeated measures analysis of variance (ANOVA) will be employed to determine whether there are any differences of symptom severity along the four time points (aim 2). Binomial logistic regression will be selected to predict a dichotomous dependent variable (i.e., existence of Long COVID) given multiple independent variables. Multiple linear regression will be used to predict continuous dependent variable (i.e., symptom severity) given multiple independent variables (aim 3).

Table 1. Long COVID Symptoms Mentioned by Example Studies and Instruments

First Author of the Studies or Instrument	Lopez-Leon	Romero-Duarte	EORTC-QLQ30	LC29
Fatigue	58%	22-34%	V	-
Pain	11%	-	V	V
Joint pain/ muscular pain	19%	15.3%	-	V
Muscle weakness	-	3.8%	-	V*
Weight loss	17%	-	-	V
Alopecia	25%	3%	-	V
Red eyes	6%	-	-	V
Cutaneous signs	12%	1.5-3.1%	-	V
Dyspnea	24%	28%	V	V
Polypnea	21%	-	-	V
Cough	19%	19.2%	-	V
Throat pain	3%	8.4%	-	V
Chest discomfort	16%	6.6%	-	V
Rib pain	-	4.5%	-	V
Headache	44%	5.3%	-	V*
Anosmia/ loss of the sense of smell	21%	-	-	-
Ageusia/ loss of the sense of taste/ dysgeusia	23%	7.2%	-	-
Paresthesia	-	3.4%	-	V
Attention disorder	27%	-	V	-
Memory loss	16%	-	V	-
Dizziness	3%	1.9%	-	V
Depression	12%	4.4%	V	-
Anxiety	13%	6.8%	V	-
Mood disorder	2%	-	V	-
Dysphoria	2%	-	-	-
Sleep disorder	11%	4.9%	V	-
Palpitation	11%	3.1%	-	-
Diarrhea	-	10.3%	V	
Constipation	-	1.8%	V	-
Abdomen pain	16%	5.4%	-	V*
N/v	58%	2%	V	-
Anorexia	11%	1%	V	-

Note. Table 1 compares the Long COVID symptoms mentioned by example studies and selected instruments. The percentage represents how many people have reported specific symptoms in the study. The check mark represents symptoms addressed in the instrument. Grey shading highlights symptoms that are not covered by EORTC QLQ30 or LC29. The instrument uses different terminology to describe the symptom.

Qualitative strand

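### The stated symptom coverage (29 of 36, three missing) does not add up or match Table 1, and dysphoria is left without a planned check

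*Combined protocol and SAP*

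**What the plan says.** In the combined protocol and SAP, under Phase two: Quantitative strand, the Instruments paragraph justifies the use of cancer questionnaires by their overlap with published Long COVID symptoms. It works from a fixed total, "among the 36 Long COVID self-perceived symptoms reported by" two cited studies, and states that "these two questionnaires covered 29 of them (about 81%), including the most frequently reported ones (table 1". The next sentence reads "Three missing symptoms that are not covered by EORTC-QLQ-C30 or LC29 are anosmia, ageusia, and palpitation", followed by "These symptoms will be checked for existence separately during the follow-ups".

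Table 1, placed after the Statistical methods paragraph, lists the symptoms against the two studies and the two questionnaires. Its note explains the marking: "The check mark represents symptoms addressed in the instrument" and "Grey shading highlights symptoms that are not covered by EORTC QLQ30 or LC29". The dysphoria row shows 2% for the cited systematic review, a dash for the six-month follow-up study, and a dash under both questionnaires.

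**The concern.** Two consecutive sentences give different numbers of uncovered symptoms. The first implies seven and the second names three. Table 1, to which the first sentence refers, shows four.

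Two things depend on this. First, the coverage figure is a main stated reason for choosing these instruments, so a reader should be able to reproduce it. Second, the separate check is the plan's way of recording listed symptoms that the questionnaires miss. A listed symptom that is neither in a questionnaire nor in the check has no scheduled assessment, so its frequency and course cannot be described under aim 2. It also cannot contribute to the outcome on existence of Long COVID under aim 3. A symptom not asked about at a follow-up cannot be reliably recovered later.

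**Working it through.** **Inputs.** From the Instruments paragraph: 36 symptoms in total, 29 covered, 3 named as missing. From Table 1: the rows and tick marks, where a row counts as covered if it has a tick, starred or not, under either questionnaire.

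**Step 1: the plan's own percentage.** 29 / 36 = 80.6%, which agrees with the stated 81% or so. The percentage was therefore computed from 29 and 36.

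**Step 2: what the text implies.**
- Uncovered: 36 − 29 = 7.
- Named and checked separately: 3.
- Unaccounted for: 7 − 3 = 4, or 4 / 36 = 11.1% of the list.
- If only three were uncovered, coverage would be 33 / 36 = 91.7%, not 81%.

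**Step 3: count Table 1.**
- Ticked under the QLQ-C30: 13 rows. Ticked under the LC29: 17 rows. Ticked under both (pain, dyspnea): 2 rows.
- Covered: 13 + 17 − 2 = 28.
- Not ticked: 4 (anosmia, ageusia, dysphoria, palpitation).
- Total: 28 + 4 = 32 rows. Coverage: 28 / 32 = 87.5%.
- Unticked and not in the separate check: 4 − 3 = 1, which is dysphoria.

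**Step 4: can another way of counting give 29 of 36?**

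| Counting rule | Covered | Total |
|---|---|---|
| As marked | 28 | 32 |
| Starred ticks treated as not covered | 25 | 32 |
| Joint/muscular pain and N/v each split in two | 30 | 34 |
| Dysphoria treated as covered | 29 | 32 |
| Text | 29 | 36 |

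No rule gives 29 of 36. The fourth row reproduces both the 29 and the three missing symptoms, since 29 + 3 = 32. It does not reproduce the 36 or the 81%, because 29 / 32 = 90.6%.

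**Step 5: could the table be short of rows?** For 29 of 36 to be right, Table 1 would lack 36 − 32 = 4 rows: one ticked (28 + 1 = 29) and three unticked (4 + 3 = 7). Even then the text would name three of seven uncovered symptoms. The conflict between seven and three lies wholly in the prose and does not depend on the state of the table.

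**The case against.** The strongest reply is that the total of 36 is the slip. The figures 29 and 3 add exactly to the 32 rows of Table 1. If the authors counted dysphoria as covered, for example together with mood disorder in the row above, nothing is left unrecorded and only the 36 and the 81% need correcting. This reading is at least as consistent with the documents as four unnamed symptoms. The shading that marks uncovered rows is also not visible in the text version of the table, so it cannot be confirmed that dysphoria was shaded. What stands is that the number of missed symptoms is uncertain. It remains true that the dysphoria row carries no tick, that a tick is how the note defines coverage, and that the text does not say dysphoria is recorded elsewhere.

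A second reply is that the plan never claims completeness. The Limitations section concedes that unlisted symptoms may be missed and offers the interviews as a remedy, the health status indicators include fever and new diagnoses, and participants can raise symptoms through the messaging group. These help only in part. Dysphoria is on the plan's own list, so the limitation on unlisted symptoms does not reach it. The interviews involve about 30 people chosen for considerable symptoms at three months, so they give no frequency for the cohort. The indicators and the messaging group are not a scheduled question about this symptom.

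Third, the effect is small and does not undermine the choice of instruments. Dysphoria is at 2% in one source, depression, anxiety and mood disorder are all ticked under the QLQ-C30 and may pick up some of it, and the table's 87.5% is higher than the stated 81%. All of this is fair and is why the point is minor.

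**Conclusion.** The counts of 36, 29 and three contradict one another, and Table 1 reproduces neither the 36 nor the 29. Dysphoria is the one identifiable symptom that the table shows as uncovered and for which no check is planned. On the text's counts up to four symptoms could be unaccounted for, but this upper figure assumes that both 36 and 29 are right, which the table does not support. The count of one assumes that the ticks in Table 1 are complete as shown.

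Three stronger readings are tempting but not supported:
- **That four symptoms will never be recorded.** Only one can be named. The other three exist only as a difference between two counts that do not match the table.
- **That participants with only such a symptom will be classed as free of Long COVID.** The Statistical methods paragraph gives no rule for when Long COVID is present, so misclassification cannot be derived.
- **That headache, abdominal pain and muscle weakness are also gaps because their ticks are starred.** A starred tick is still a tick. If the star belongs to the note "The instrument uses different terminology to describe the symptom", it says the symptom is addressed under another name. Asking about these by name would be a preference, not a correction.

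Severity: minor. The inconsistency is certain and its demonstrable effect on the data is small.

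**What to change.** Recount the symptoms from the two cited studies so that the Instruments paragraph and Table 1 show the same total, the same number covered and the same uncovered symptoms. Restate the coverage percentage from that count. Add dysphoria, and any other symptom the recount shows as uncovered, to the existing separate existence check at each follow-up. If the authors regard dysphoria as covered by a questionnaire item, tick it in Table 1 and say which item covers it; in that case no extra question is needed.

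The cost is one or a few additional yes/no items per follow-up, a corrected sentence and a corrected percentage. Sample size, schedule and analysis methods are unaffected.

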
關鍵詞 (Keywords) : COVID-19, Long COVID, long-term effects, mixed-methods, health-related quality of life, longitudinal cohort study

Aims

The overarching goal of this proposed project is to explore the Long COVID and associating factors in Taiwan. In the proposed research project, we intend to investigate both ongoing and post-COVID-19 syndrome defined by NICE guideline and referred these symptoms as Long COVID. Building upon the overarching goal, the specific aims of this research project are to (1) integrate the state of science of Long COVID, (2) describe the changes of various symptoms and HRQOL after 3, 6, 9, and 12 months of COVID-19 diagnosis, (3) explore predicting factors of the existence and severity of Long COVID, and (4) explore how patient experienced COVID-19 symptoms.

Introduction

Starting from the beginning of 2020, the COVID-19 pandemic has already affected more than one billion people with over three million deaths globally [1]. In Taiwan, about ten thousands covid-19 cases were confirmed in mid-June, 2021, and the case number continues to grow [2]. While a lot of individuals diagnosed with COVID-19 completed the treatment course of the acute phase and returned to their community, a considerable portion of COVID-19 survivors continuously experienced complicated, distressing, and multiple long-term symptoms weeks to months after COVID-19 diagnosis [3, 4]. These long-term symptoms sometimes may be labeled as Long COVID, post-COVID symptoms, or ongoing symptoms and have profound impact on individuals health, function, and quality of life [5, 6]. Thus developed guidelines stress the importance of monitoring and managing Long COVID continuously [7]. However, the symptom profile is still vague and the guideline is left to be scrutinized.

Symptom profile of Long COVID

Although it is expected that the acute symptoms of COVID-19 last about a week [8], researchers have warned that more than 50 long-term symptoms or signs can be experienced by COVID-19 survivors weeks after diagnosis [3].

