Sampling and Recruitments. Inclusion criteria are individuals who are (1) at least 20 years-old and (2) diagnosed with COVID-19 within six months. Exclusion criteria are individuals who (1) are still in the active phase of COVID-19 infection (i.e., diagnosed within 4 weeks) and (2) have cognitive impairment or other issues that prevents them from doing self-ratings of symptoms via phone interviews. The estimated sample size is about 98 subjects based on G*Power 3.1.9.4 calculation (effect size $f^2=0.15$, $\alpha=0.05$, $\beta=0.2$, 6 predictors). Considering the loss of follow-up rate of 20%, 118 subjects are needed.

Potential subjects will be identified through the following strategies: (1) searching the intranet of participating medical institutions (e.g., National Taiwan University Hospital, National Yang Ming Chiao Tung University Hospital and Min-Sheng General Hospital), (2) recruitment messages posting on social media, and (3) referrals from collaborating healthcare providers. After participants fill out the online questionnaire, research assistant will approach potential subjects via phone to explain the research, explore their willingness, and screen for eligibility. Individuals who are eligible and agree to participate in the study will receive documents of study information and consent form by mail. Participants are required to mail back the signed inform consents.

Upon the receiving the signed inform consents, the subjects will be followed immediately to confirm participation and collect demographic data. They will then be regular followed up at 3 (for those who are participated within 3 months of COVID diagnosis), 6, 9, and 12 months (T1-4) from the diagnosis of COVID-19. During these regular follow-ups, subjects will need to report health status indicators and rate their symptom severity and HRQOL based on selected instruments. Subjects will have access to a line group managed by the research team. They can communicate with the research team regarding any issues of research or symptoms through line group. All data collection will be occurred via online questionnaire, phone or video call interview (e.g., +Google meet or line video call). Paper documents, such as inform consents, will be stored in the locked cabin located at National Taiwan University School of Nursing. Electrical data will be managed and stored using Redcap and encrypted Dropbox.

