This project will be the first to address long-term effects of COVID-19 from both subjective and objective aspects. In addition to its innovation, this project responds to real time issues as a growing number of COVID-19 survivors emerged in Taiwan. The society, health system, families, and survivors will soon encounter the challenges and burden of managing Long COVID. This research project can help monitor long-term effects and serves as a base for early identification and timely interventions. It also provide important reference for relevant policy-making.

Table 4. Timeline of the Proposed Research Project

Process	months	Year/ months	2021		2022				2023		
			8-9	10-12	1-3	4-6	7-9	10-12	1-3	4-6	7
Phase 1: preparation and systematical review											
Preparation: formulating research team		X									
Preparation: IRB		X									
Systematical review: literature search and analysis		X	X								
Systematical review: manuscript writing				X							
Phase 2: quantitative strand											
Quantitative strand: recruitment			X	X							
Quantitative strand: data collection			X	X	X	X	X	X			
Quantitative strand: data analysis							X	X	X		
Quantitative strand: preliminary report										X	
Phase 3: qualitative strand											
Qualitative strand: recruitment			X	X	X	X					
Qualitative strand: data collection			X	X	X	X	X				
Qualitative strand: data analysis				X	X	X	X	X	X		
Qualitative strand: preliminary report										X	
Mixed-methods: interpretation and final report										X	

Reference

1. WHO. *Coronavirus disease (COVID-19) pandemic*. 2021; Available from: <https://www.who.int/emergencies/diseases/novel-coronavirus-2019>.
2. Center, T.D.C. 2021 [cited 2021 6/16]; Available from: <https://www.cdc.gov.tw/>.
3. Lopez-Leon, S., et al., *More than 50 Long-term effects of COVID-19: a systematic review and meta-analysis*. Available at SSRN 3769978, 2021.
4. Romero-Duarte, Á ., et al., *Sequelae, persistent symptomatology and outcomes after COVID-19 hospitalization: the ANCOHVID multicentre 6-month follow-up study*. BMC medicine, 2021. **19**(1): p. 1-13.
5. Walle-Hansen, M., et al., *Health-related quality of life, functional decline, and long-term mortality in older patients following hospitalisation due to COVID-19*. BMC geriatrics, 2021. **21**(1): p. 1-10.
6. Halpin, S.J., et al., *Postdischarge symptoms and rehabilitation needs in survivors of COVID-19 infection: A cross-sectional evaluation*. Journal of medical virology, 2021. **93**(2): p. 1013-1022.

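### The only test named for aim 2 needs a 3-month rating that later enrolees never get, and the plan has no missing-data rule

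*Combined protocol and SAP*

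**What the plan says.** The second specific aim is to "describe the changes of various symptoms and HRQOL after 3, 6, 9, and 12 months of COVID-19 diagnosis".

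Under Sampling and Recruitments, participants must be "diagnosed with COVID-19 within six months", and people within 4 weeks of diagnosis are excluded. Entry is therefore open from 4 weeks to six months. Participants are then "regular followed up at 3 (for those who are participated within 3 months of COVID diagnosis), 6, 9, and 12 months", labelled T1 to T4. The 3-month visit is conditional on early entry; the other three apply to everyone.

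Under Statistical methods, a one-way "repeated measures analysis of variance (ANOVA) will be employed to determine whether there are any differences of symptom severity along the four time points". Descriptive statistics are planned alongside it: "In addition to use descriptive statistics to describe the characteristics of participants and symptoms". The paragraph says nothing about missing ratings, whether by imputation, a model for incomplete data or a rule on who enters the test.

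The nearest related text is the sample-size allowance, "Considering the loss of follow-up rate of 20%, 118 subjects are needed", and the retention measures in the Limitations section. Both concern people who drop out. Neither covers a visit that was never scheduled.

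**The concern.** The visit schedule and the analysis method do not fit together. Someone who joins four months after diagnosis can attend every scheduled visit and still lack T1. The classical one-way repeated-measures ANOVA needs a complete row per person, so it would exclude that participant, together with anyone who misses a single visit.

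Three things are at stake.

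- **Population.** The test would describe change only in early, fully followed enrolees, although the cohort is defined more widely.
- **Precision.** Late enrolees supply 6-, 9- and 12-month ratings, and the protocol's own account of the knowledge gap stresses symptoms beyond six months. The test would not use these ratings.
- **Bias.** If entry time or retention is related to symptoms, the estimated change could be biased. The documents do not show whether it is.

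The descriptive statistics are unaffected and can use every rating.

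**Working it through.** **The plan's own sample size.** The 98 reproduces as the overall F test of a regression with 6 predictors (f² = 0.15, two-sided α not involved, α = 0.05): power is 0.8035 at N = 98 and 0.7984 at N = 97. The 118 is 98 × 1.2 = 117.6. This calculation serves the regression in aim 3; no sample size is given for the aim 2 ANOVA.

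**Inputs.** From the documents: 118 enrolled, 20% loss, entry from 4 weeks to six months, T1 only if joining within 3 months. Assumed, because the documents do not give them: the early share s, a rating SD of 1, an exchangeable within-person correlation ρ = 0.5, and loss spread evenly before T2, T3 and T4.

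**Early share under even entry.** s = (13 − 4)/(26 − 4) = 9/22 = 0.41, in weeks.

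**Counts.**
- Complete four-point cases: 118 × s × 0.8.
- Late enrolees with complete 6-, 9- and 12-month ratings: 118 × (1 − s) × 0.8.
- At s = 0.41: 118 × 0.409 × 0.8 = 38.6 and 118 × 0.591 × 0.8 = 55.8.
- Fewer than half of the 118 are analysed when s is below 0.5/0.8 = 0.625.

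**Standard error of the 6-to-12-month change (T4 − T2).**
- Complete cases: √(2(1 − ρ)/n). With ρ = 0.5 this is √(1/n); at n = 38.6 it is 0.161.
- Mixed model: sum X′V⁻¹X over all attendance patterns, invert, and take the contrast. This gives 0.1004 to 0.1006 at shares from 25% to 75%. Adding enrolment timing as a covariate does not change it.
- Ratio at s = 0.41: 0.161/0.1005 = 1.60.

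**Detectable 6-to-12-month change.** Paired t test, two-sided 0.05, 80% power; with ρ = 0.5 the SD of the difference is 1.

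| Early share | Analysed of 118 | Late completers left out | SE, complete case | SE ratio to mixed model | Detectable change (SD) |
|---|---|---|---|---|---|
| 25% | 24 | 71 | 0.206 | 2.05 | 0.60 |
| 41% | 39 | 56 | 0.161 | 1.60 | 0.46 |
| 60% | 57 | 38 | 0.133 | 1.32 | 0.38 |
| 75% | 71 | 24 | 0.119 | 1.18 | 0.34 |
| 90% | 85 | 9 | 0.108 | 1.08 | 0.31 |
| 100% | 94 | 0 | 0.103 | 1.03 | 0.29 |

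**Sensitivity.** At the 41% share the ratio is 1.61, 1.60, 1.59 and 1.59 for ρ = 0.3, 0.5, 0.7 and 0.9.

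**The 3-to-12-month change (T4 − T1).** At shares of 25%, 41%, 60% and 75% the ratios are 1.26, 1.20, 1.14 and 1.10 without the enrolment covariate, and 1.23, 1.18, 1.12 and 1.09 with it.

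**A simpler comparator.** A three-point analysis (6, 9, 12 months) of the 118 × 0.8 = 94.4 retained participants has SE √(1/94.4) = 0.103 for the 6-to-12-month change, against 0.1005 for the mixed model.

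**The case against.** The mismatch in the text is hard to dispute. The stronger objections concern its size and the remedy.

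- **The early share is unknown and could be high.** At 90% the ratio is only 1.08, and at 100% it is 1.03. This stands, and the table shows that end too.
- **The 25% case is strained.** The qualitative strand seeks about 30 people with considerable symptoms at the three-month follow-ups. At 25%, only 118 × 0.25 = 29.5 people are scheduled for T1. If 80% of early enrolees had such symptoms and all agreed, 30/0.8 = 37.5, so 38 early enrolees (32% of 118) would be needed. This points away from the worst case, although the abstract words entry to that strand more loosely.
- **The timeline gives little help.** The Introduction reports "about ten thousands covid-19 cases were confirmed in mid-June, 2021". If the Table 4 row "Quantitative strand: recruitment" starts in October 2021, as the broken table appears to show, none of those cases could have a T1. But by mid-December they would be past the six-month entry limit, and later cases could join early. It does not fix the share.
- **The largest ratios are for a contrast the plan does not name.** The planned test is an overall comparison across four points. For the 3-to-12-month contrast the gain is modest, because no model recovers a T1 that was never taken. This stands. The 6-to-12-month change is nevertheless part of aim 2 and is where the unused data lie.
- **Exclusion is inferred.** The plan does not state listwise deletion. True, but it is how the named method normally works, and leaving it open means the choice among different analysis populations is made after the data are seen.
- **A mixed model is not the only repair.** A four-point ANOVA labelled as early enrolees only would be coherent, and the three-point analysis nearly matches the mixed model for later change. The mixed-model figures also treat the covariance as known and exchangeable, so they are slightly optimistic for an unstructured fit.

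**Conclusion.** The concern holds. The only test named for aim 2 requires a rating that the schedule withholds from everyone who joins after 3 months, and nothing elsewhere in the plan resolves this. That conclusion follows from the text and needs no assumption beyond the ordinary behaviour of the method.

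The size depends on the early share, which is an assumption throughout. Over shares of 25% to 75%, about 24 to 71 of 118 would be analysed, and the standard error of the 6-to-12-month change would be 2.05 to 1.18 times what the collected data allow. Under even entry the figures are 39 of 118 and 1.60. Above about 90% the practical loss is small. Bias is possible but not shown. This should be fixed before analysis; it does not threaten the data themselves or the descriptive results.

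**What to change.** Replace the repeated-measures ANOVA with a linear mixed model on all available ratings: REML, visit as a categorical fixed effect, unstructured within-person covariance, and enrolment timing (within 3 months or later) as a covariate. Alongside it:

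- report the 6-, 9- and 12-month means by enrolment group as a check;
- report the contrasts with month 3 in early enrolees alone as well;
- state the missing-data rule and who enters the aim 2 test.

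If a simpler method is preferred, a three-point analysis at 6, 9 and 12 months in all retained participants is acceptable for the later change.

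The cost is analysis-plan wording and standard software, with no extra data or participants. The drawback is that the mixed model assumes ratings are missing at random. Its contrasts with T1 further assume that, given the model, late enrolees would have behaved like early ones at 3 months. That cannot be checked, which is why the early-enrolee-only contrast is also needed.
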